#### 7.1.7.3 Glucose ultrafiltration efficiency

Based on data gathered from the efficacy evaluation treatments during the home treatment phase of the study glucose ultrafiltration efficiency will be calculated. For each patient the average glucose UF efficiency (ml UF / g glucose absorbed) from the per protocol efficacy evaluation treatments in each arm will be used for the analysis. A paired comparison between the glucose UF efficiency achieved with the Carry Life® UF treatment ( $GlucEff_{CL}$ ) and the control CAPD dwell ( $GlucEff_{CAPD}$ ) per protocol treatments will be conducted. The average paired difference and the associated 95% CI will be calculated. Further, a t-test will be used to demonstrate that the Carry Life® UF treatment has a higher a glucose ultrafiltration efficiency than the control 2.27% CAPD dwell. The difference in glucose UF efficiency for each Carry Life® UF glucose dose and each fill volume compared to the control CAPD dwell will be summarized.

#### 7.1.7.4 Peak dialysate concentration

During the in-clinic phase of the study the peak dialysate glucose concentration during the Carry Life® UF treatments will be determined from hourly dialysate sampling points, for each glucose dose. For this secondary endpoint, each subject is expected to have dialysate glucose data (T1h to T5h) from one in-clinic treatment at each Carry Life® UF glucose dose.

The average peak glucose dialysate concentration (in %; gram glucose per 100 ml fluid) for each glucose dose of the Carry Life® UF in-clinic treatments and the associated 95% CI will be calculated for the PP population. Further, a t-test will be used to demonstrate that the peak dialysate glucose concentration during the Carry Life® UF treatment is lower than 2.27%. The peak glucose concentration at each fill volume will be summarized.

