-------------	---

	
A flow diagram of the study design is shown below (Figure 1). Refer to Table 1 for the schedule of activities at each visit.
 
Figure 1. Study flow chart
  <pre> graph LR     A[Screen. & Consent *] --> B[1 PET + 2 CLUF]     B --> C[Randomization]     C --> D[Grp. A]     C --> E[Grp. B]     C --> F[Grp. C]     C --> G[Grp. D]     D --> H[Control]     D --> I[T]     D --> J[CLUF 11 g/h]     E --> K[Control]     E --> L[T]     E --> M[CLUF 15 g/h]     F --> N[T]     F --> O[CLUF 11 g/h]     F --> P[Control]     G --> Q[T]     G --> R[CLUF 15 g/h]     G --> S[Control]   </pre> 
Abbreviations: CLUF = Carry Life® UF; Grp. = Group; PET = peritoneal equilibration test; Screen. = Screening; T = Transition to home phase with device training.    * A run-in period of at least two weeks may be performed in order to make an approved adjustment the PD prescription so that it can meet the study inclusion criteria

STUDY FOLLOW UP	The subject will be followed up for one (1) week for new or continuing AEs after the end-of-study visit. The follow-up will be in the form of a phone call or a physical meeting as required.
NUMBER OF SUBJECTS	Approximately 25 patients will be enrolled with a goal of 19 completing the study per protocol.
STUDY POPULATION	Adult subjects with end-stage kidney disease (ESKD) treated with CAPD.

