### 3.7 EXPLORATORY STUDIES WITH MAINTAINED INTRAPERITONEAL GLUCOSE CONCENTRATION

Therapeutic concepts similar to the Carry Life® UF system such as continuous flow PD (CFPD) and steady concentration PD (SCPD) have been described in the literature. The features of CFPD are that the IP volume is fixed and that dialysate rapidly and continuously flows in and out of the peritoneal cavity, creating a stable IP glucose concentration. Studies performed with CFPD have demonstrated that CFPD results in a significantly higher UF volume compared to standard PD therapies.

In the study on adult PD patients by Freida *et al.* the UF volume in the PET (2.27% glucose), achieved 270 mL, whereas the mean UF in CFPD was 587 mL with a 1.36% PD solution. UF and net sodium removal extrapolated to eight hours of treatment was also much higher with CFPD (1175 mL UF; 212 mmol sodium removal) compared to 8 hours APD treatment APD (427 mL UF; 66 mmol sodium removal). Glucose absorption was not significantly different between the CFPD and APD session but the glucose UF efficiency (UF/absorbed glucose) was higher with the CFPD (33.5 mL/g) compared to APD (11.4 mL/g).

In a study by Pérez-Díaz a PD treatment concept close to that of the Carry Life® UF system was used. In the study a 50% glucose solution, at a dose of 20–30 g/h, was continuously administered to the IP fluid during four-hour dwells in PD patients with symptomatic fluid overload that could not be adequately treated with available PD methods. IP glucose concentrations at the end of the PD dwell was  $1.89 \pm 0.42\%$ . The highest IP glucose concentration was 2.7%. The treatment reversed all episodes of fluid overload, and serum glucose levels were stable and remained within safe levels during the study. The SCPD achieved high UF volumes in the four-hour sessions ( $653 \pm 363$  mL/4 h) and achieved twice the UF volume compared to the patients' PET tests ( $300 \pm 251$  mL/4 h) and

6 times that of their regular PD regime ( $100 \pm 123$  ml/4 h). The achieved UF volumes varied in the study participants, despite identical treatments being performed, which was partly explained by a correlation of UF to fluid overload. The conclusion of the Pérez-Díaz study was that SCPD may provide an effective and safe tool to manage UF in PD, opening new therapeutic possibilities to optimize and increase the flexibility of PD treatments.

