**Secondary endpoint hypotheses**

**Peritoneal sodium removal:** The peritoneal sodium removal achieved with the Carry Life® UF system is larger than the peritoneal sodium removal achieved with CAPD using a 2.27% glucose PD solution during a 5-hour treatment.

Hypothesis:

H0:  $\mu_{CL} \leq \mu_{CAPD}$

H1:  $\mu_{CL} > \mu_{CAPD}$

Where  $\mu_{CL}$  is the average paired Carry Life® UF peritoneal sodium removal and  $\mu_{CAPD}$  is the average paired CAPD peritoneal sodium removal.

**Glucose UF efficiency:** The glucose UF efficiency (ml UF volume / g glucose absorbed) achieved with the Carry Life® UF system is higher than the glucose UF efficiency achieved with CAPD using a 2.27% glucose PD solution during a 5-hour treatment.

Hypothesis:

H0:  $\mu_{CL} \leq \mu_{CAPD}$

H1:  $\mu_{CL} > \mu_{CAPD}$

Where  $\mu_{CL}$  is the average paired Carry Life® UF glucose UF efficiency and  $\mu_{CAPD}$  is the average paired CAPD glucose UF efficiency.

Peak dialysate glucose concentration:

H0: PeakCL dialysate glucose concentration  $\geq$  2.27%

H1: PeakCL dialysate glucose concentration  $<$  2.27%

Where peakCL is the highest measured dialysate glucose concentration during the Carry Life® UF treatment (T1h to T5h).

AEs and SAEs:

There is no statistical test for the safety endpoint. The AEs will be tabulated and described in detail.

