### 5.3 CLAIMS OF PERFORMANCE OF THE DEVICE

Claims and intended performance of the investigational device to be verified include:

- A larger UF volume can be obtained compared to a standard 2.27% glucose CAPD dwell.
- A larger sodium removal can be obtained compared to a standard 2.27% glucose CAPD dwell.
- The device maintains the intraperitoneal glucose concentration throughout the treatment.
- The glucose concentration is maintained below 2.27% i.e., below the glucose concentration of a medium strength glucose PD solution.
- The system prevents increases in intraperitoneal volume by hourly drainage of approximately 180 ml of dialysate.
- The glucose UF efficiency (ml UF / g glucose absorbed) is improved compared to a standard 2.27% glucose CAPD dwell.

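### The t-test on peak dialysate glucose supports a statement about the average peak, not by itself the section 5.3 claim that glucose is maintained below 2.27% during treatment

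*Protocol*

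**What the plan says.** Protocol section 5.3 gives the performance claims that the investigation is meant to verify. One reads: "The glucose concentration is maintained below 2.27% i.e., below the glucose concentration of a medium strength glucose PD solution".

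Section 5.2, under the secondary endpoint hypotheses, sets a null hypothesis of a peak at or above 2.27% against an alternative of a peak below it. It defines the peak within a treatment: it "is the highest measured dialysate glucose concentration during the Carry Life® UF treatment (T1h to T5h").

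Section 7.1.7.4 then names the quantity to be estimated with a 95% confidence interval in the per-protocol population: "The average peak glucose dialysate concentration (in %; gram glucose per 100 ml fluid) for each glucose dose". It adds that "a t-test will be used to demonstrate that the peak dialysate glucose concentration" during treatment is below 2.27%.

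No criterion for individual treatments is set, whether a proportion below the limit, a tolerance limit or a rule on the maximum. Section 7.1.9 plans mean, median, SD, minimum, maximum and number of observations for continuous data, and section 7.1.12 plans full listings.

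**The concern.** The claim describes what happens during treatment and the peak is defined treatment by treatment, but the test looks only at the centre of the distribution of peaks. A mean below 2.27% can coexist with a material share of treatments at or above it.

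This matters because the stated rationale concerns exposure. Section 6.2.7.2 links hypertonic solutions to membrane deterioration and higher concentrations to faster glucose uptake. Section 6.2.11.3 argues that starting with a 1.36% solution exposes the membrane to less glucose than a 2.27% solution would. A patient whose own dialysate passes 2.27% is not helped by a low group mean. If the claim were later read as covering treatments in general, the planned test would not carry it.

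**Working it through.** **Inputs**
- Limit: 2.27% (sections 5.2, 5.3 and 7.1.7.4).
- One in-clinic treatment per subject and dose, one peak per treatment (section 7.1.7.4).
- Number of treatments: the synopsis says "Approximately 25 patients will be enrolled with a goal of 19 completing the study per protocol". So n = 19 to 25 is used. The 19 is a target for finishing the whole study, so the in-clinic number may differ.
- At 15 g/h n may be smaller, because section 6.2.2 omits that treatment when 11 g/h yields 1.0 L or more. The documents do not say how often; 12 and 15 are used as assumed values.
- Level: none is stated for this test. One-sided 0.025, the level of the primary test, is assumed, with one-sided 0.05 as the range.
- SD of peaks: not given. The boundary result below does not need it.

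**The plan's own figure.** No sample size or power is stated for the peak test. The 19 comes from the primary endpoint, and the formula printed in section 7.1.1 returns it: (z_α + z_β)² × 330² / [2 × (400 − 250)²] = 18.99 with unrounded normal quantiles, rounded up to 19.

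**Share at or above 2.27% when the test is just significant.** A one-sample t-test reaches the boundary when (2.27 − mean)/SD = t(1−α, n−1)/√n. With normal peaks the share at or above the limit is then Φ(−t/√n), whatever the SD.

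| n | t (one-sided 0.025) | t/√n | share ≥ 2.27% |
|---|---|---|---|
| 12 | 2.201 | 0.635 | 26.3% |
| 15 | 2.145 | 0.554 | 29.0% |
| 19 | 2.101 | 0.482 | 31.5% |
| 25 | 2.064 | 0.413 | 34.0% |

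At one-sided 0.05 the shares are 34.5% (n = 19) and 36.6% (n = 25).

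**How often the test succeeds for a given true share.** Simulation with normal peaks, 200,000 trials per setting, one-sided 0.025:
- True share 20%: significant in 93% of trials at n = 19 and 98% at n = 25.
- True share 25%: 79% and 90%.
- True share 31.5%: 51% at n = 19.

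**Not a ceiling.** Without normality the share can be higher. With 15 of 19 peaks exactly at 2.27% and the other four 0.3 percentage points lower, the test is still significant.

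**What the pilot suggests.** Section 4.1 gives levels of about 1.6% at 11 g/h and 1.9% at 14 g/h, with no SD of peaks. Taking these as mean peaks, with SDs of 0.2%, 0.3% and 0.4% as assumptions:
- Mean 1.9%: (2.27 − 1.9)/SD = 1.85, 1.23 and 0.93, giving shares of 3.2%, 10.9% and 17.7%.
- Mean 1.6%: shares of about 0%, 1.3% and 4.7%.

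**What a count could show.** With zero exceedances the upper limit of the two-sided 95% Clopper–Pearson interval is 1 − 0.025^(1/n): 17.6% at n = 19, 13.7% at n = 25, and 21.8% and 26.5% at n = 15 and 12.

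**The case against.** The strongest reply is that section 5.3 nowhere says in every treatment or in every patient. Its comparative claims on ultrafiltration, sodium and glucose efficiency are also worded about the device and tested on means. The matching objective in section 5.1.2 is only to evaluate whether the peak is lower than the concentration of a 2.27% solution, and a one-sample t-test suits that. Exceedances would also be visible, since the SD, the maximum and full listings are planned.

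Much of this stands. The t-test is valid for the average peak and should stay. It would be wrong to say that the planned output is silent on exceedances, because a mean and SD allow a rough estimate and the maximum shows whether any occurred. But those descriptives feed no claim, and a maximum does not give a proportion. This claim also differs from its neighbours: it says that a level is kept below a fixed limit, and its variable is the highest value within a treatment.

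A reader might infer three stronger things that the documents do not support:
- That about a third of treatments will exceed the limit, or that a third is the most the test would tolerate. It is neither; it is the boundary value under normality and an assumed level.
- That the SD of 0.42% in section 3.7, or the sentence "The highest IP glucose concentration was 2.7"%, forecasts what will happen here. That SD describes end-of-dwell values, and both figures come from a cited study dosing 20–30 g/h. The device's own pilot stayed between 1.6% and 2.2% at doses up to 20 g/h (section 3.8).
- That the protocol makes a significant t-test sufficient to declare the claim verified. No section states such a rule.

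**Conclusion.** The point holds in limited form. A significant result in section 7.1.7.4 supports the statement that the average peak is below 2.27%. It does not by itself verify that the concentration is maintained below 2.27% during treatment.

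The size of the gap, 31–34% of treatments at n = 19–25 and 26–29% at n = 12–15, rests on near-normal peaks, an assumed one-sided 0.025 level and a result exactly at the boundary. The pilot levels point to fewer exceedances, but without an SD of peaks, and at 14 rather than 15 g/h for the higher dose, they do not settle how many.

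Severity is minor to moderate: this is a secondary endpoint, but one tied to an explicit performance claim, and the mismatch lies in text that the protocol itself fixes.

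**What to change.** 1. Keep the t-test, and reword the section 5.3 claim that it supports to say that the average peak glucose concentration is below 2.27%.
2. Add to section 7.1.7.4, for each dose, the number and proportion of treatments with any T1h–T5h sample at or above 2.27%, with a Clopper–Pearson 95% confidence interval.
3. Word any statement about individual treatments from that proportion and its upper limit. Even with no exceedances, the data would leave open a true rate of up to about 18% at n = 19 or 14% at n = 25, so an unqualified per-treatment claim would remain out of reach.

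The cost is one extra table from samples already planned, and a milder claim. No visit, sample or change in sample size is needed.

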#### 7.1.8 Statistical analysis of exploratory endpoints

A basic comparison peritoneal removal of creatinine and urea as well as of the weekly UF based on patient diary will be performed across the arms of the study.

#### 7.1.9 Description and inference

Aggregated continuous data will be presented in terms of mean, median, standard deviation, minimum and maximum, and number of observations. Aggregated categorical data will be presented using frequency tables.

#### 7.1.10 Missing values

Subjects who drop out of the study will be characterized and compared to those remaining in the study based on demographics and co-morbidities.

#### 7.1.11 Additional summaries

All demographic and baseline characteristics captured in the CRF will be summarized for all populations included in the analysis (ITT and PP as defined for all endpoint analysis see 7.1.1) and those that are not, and descriptive statistics will be presented when applicable. The frequency and distribution of missing data for any characteristic will also be described.

#### 7.1.12 Listings

All data captured in the study will be listed. This will include outcomes not included in the summaries such as concomitant medication and medical history.

## 8 DATA MANAGEMENT

---

### 8.1 PROCEDURES USED FOR DATA REVIEW

During the site initiation visit, training on the CIP and eCRF will be performed to ensure familiarity with the documents and eCRF completion of good quality. Data entries in the eCRF will be monitored during the clinical investigation against the source data and verified for accurateness and completeness. Data entered to the eCRF are subject to system-implemented edit-checks and additional manual checks by data management as per data management plan and data validation plan. Any queries generated regarding missing, inconsistent, or illogical data in the eCRF will be followed up by the site and verified by the monitor or data management. The eCRF is also reviewed for missing data early in the clinical study to reduce systematic data errors, allowing all required data to be captured. Any corrections made in the CRF will be tracked by the audit trail and the eCRF is signed by the Investigator at completion.

During the clinic visits data may be recorded in the patient file and on source data worksheets before entry into the eCRF. Blood and urine samples will be analyzed at the local laboratory used by the site and the result entered into the eCRF. For the dialysate samples, the study will use a central laboratory that perform all dialysate laboratory analyses. Dialysate data do not need to be analyzed until the end of the study and will not be entered into the eCRF. After review of all entered data was concluded, all queries have been resolved and all pages have been signed electronically by the principal investigators, the eCRF will be locked.

During the home treatment phase subjects will record clinical measurements and solution weights daily. Primarily, the subjects will enter the data (e.g., weight and blood pressure) into a mobile application. The data entered into the App will be transferred directly into the eCRF and there is no additional source documentation expected and thus these values are not subject to source data verification through the monitor. In case a subject does not use the App, but records data in a paper-based diary instead, the data are entered by dedicated site staff into eCRF and are subject for source data verification. However, in case of out of limit measurements the site is going to be alerted by means of a query and is going to follow-up with the patient to verify and discuss the entered data for any potential error. When copies of original source documents as well as printouts of original electronic source documents are retained, these shall be signed and dated by a member of the investigation site team with a statement that it is a true reproduction of the original source document. Copies of the source data shall remain at the clinical investigation site when the investigation is completed allowing an independent account of the investigation process.

The data from the eCRF will be managed in an EDC system. The EDC database will be programmed to use the input data from the eCRF to calculate output data including the endpoint measures (e.g., UF volume, peritoneal removal of the substances analyzed in the dialysate, and glucose efficiency). To be able to perform the calculation the following constants will be used:

- Glucose molecular weight: 180.16 g/mol.
- 50% glucose solution concentration: 0.5 g/ml.
- Density 50% glucose solution: 1.2235 g/ml.

Additionally plastic weights of solution bags and drain bags may be pre-weighed and used to calculate fill and drain volumes.

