### 2.1 SUMMARY DESCRIPTION OF THE INVESTIGATIONAL DEVICE AND ITS INTENDED PURPOSE

The intended use of the Carry Life® UF system is for peritoneal dialyses (PD) and ultrafiltration (UF). The therapeutic concept of the Carry Life® UF system is to maintain a stable intraperitoneal (IP) glucose concentration and thereby achieving a stable peritoneal UF. The Carry Life® UF system is indicated for PD and UF in adult patients with end-stage kidney disease (ESKD). Treatment with the Carry Life® UF system is prescribed by the treating physician and intended for use in dialysis clinics or in the home environment.

The Carry Life® UF system consists of the following parts:

[figure not shown]
- Carry Life® UF Cycler.
- Carry Life® UF Line set.
- Carry Life® UF Carrying bag.
- Carry Life® UF Storage bag.
- Battery and battery charger.

Treatment with the Carry Life® UF system also requires the following products:

- A standard PD catheter.
- A standard Baxter MiniCap extended life PD transfer set with twist clamp for access to the intraperitoneal catheter.
- A PD belt (Frank Stubbs).
- A 13.6 mg/ml glucose (1.36 %), 1.5 or 2L Baxter Peritoneal Dialysis solution.
- A 500 mg/ml, 500 ml Glucose Fresenius Kabi solution for infusion.

In this clinical investigation, subjects will already have a standard PD catheter and an extension set, and use the PD bags provided in their standard PD prescription. For participation in this clinical investigation, the Sponsor, or their designee, will provide the PD belt, and the glucose PD solution.

The Carry Life® UF Cycler with line set and glucose bag attached is illustrated in Figure 3.

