**Table 7. The tests methods, recording and analysis of variables**

Test/assessment	Required measurements	Recording	Analysis	Source data
PD fill volume	Weight of full PD bags with or without outer wraps. Weight of plastic material (may be predetermined).	In-clinic visits, PET, and Carry Life® UF treatments: Home phase efficacy evaluations treatments (control and Carry Life® UF).	Calculated by electronic data capture (EDC): The weight of full PD bags minus weight of the plastic material.	Work sheets for measured data and eCRF for calculated data.
Drained volume	Weight of drain bags. Weight of plastic material (may be predetermined)	All CAPD dwells and Carry Life® UF treatments during home phase.	Calculated by EDC: The sum of all volumes drained for each treatment, including all dialysate sample volumes.  The drained volume in each drain bag is calculated as the weight of the drain bag minus the weight of the plastic material.	Work sheets for measured data and eCRF for calculated data.
Treatment time (hours)	Time for end of peritoneal fill and start of peritoneal drain.		Calculated by EDC: Time between "end of peritoneal fill" and "start of peritoneal drain"	Work sheets for measured data and eCRF for calculated data.
Glucose volumeexact	Weight of full glucose bag with or without outer wrap. Weight of used glucose bag. Weight of plastic material (may be predetermined)	Carry Life® UF in-clinic treatments and Carry Life® UF efficacy evaluation treatments (ml).	Calculated by EDC; Weight of full glucose bag minus weight of used glucose bag (g) divided by the density of the 50% glucose solution (1.2235 g/ml).	Work sheets for measured data and eCRF for calculated data.
Glucose volumeapprox for Carry Life® UF home treatments other than efficacy evaluation days (ml)	None, nominal volume for the 5 hour Carry Life® UF treatment at each dose 110 ml (11 g/h) and 150 ml (15 g/h) is used.	Daily during Carry Life® UF arm	N/A	eCRF (prescribed Carry Life UF glucose dose).

Test/assessment	Required measurements	Recording	Analysis	Source data
UF volumeexact (ml)	PD fill volume. Glucose volume. Drained volume.	In-clinic visits, Home phase efficacy evaluations treatments	Calculated by EDC; Drained volume-PD fill volume - Glucose volume exact .	Work sheets for measured data and eCRF for calculated data.

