UF volumeapprox. (ml)	PD fill volume. Glucose volume. Drained volume.	All dwells/Carry Life® UF treatments during home phase.	Calculated by EDC; Drained volume-PD fill volume - Glucose volume approx.	Work sheets/electronic patient-reported outcome measures (ePROM) for measured data and eCRF for calculated data.
UF rate (ml/kg body weight/treatment)	UF volume exact . Body weight before treatment.	In-clinic phase, Carry Life® UF treatments.	Calculated by EDC; UF volume exact /Body weight before treatment.	Work sheets for measured data and eCRF for calculated data.
UF volume % increase	UF volume exact	End of In-clinic phase	Calculated by EDC; ([UF volume exact Visit4/ UF volume exact Visit3]-1)*100	eCRF
Dose determination	UF volume % increase	End of In-clinic phase	Determined by EDC according to dose determination algorithm.	
Dialysate glucose concentration	Glucose concentration in drain samples	In-clinic phase, PET, and Carry Life® UF treatments: PET: T0, T1h, T2h, T4h Carry Life UF: T0, T1h, T2h, T3h, T4h, T5h, peritoneal drain	Laboratory analysis	Laboratory data
Peak dialysate glucose concentration	Glucose concentration in drain samples	In-clinic phase, Carry Life® UF treatments: T1h, T2h, T3h, T4h, T5h	Data analysis	N/A
PET	Sodium and creatinine concentration in dialysate.	PET, at T0, T1 and T2 T4	D/P creatinine  Transfer type determined as D/P creatinine at 4h Low: 0.34-0.50 Low average: 0.50-0.65 High average: 0.65-0.81 High: 0.81-1.03  Sodium dip: Dialysate sodium: T1 minus T0	Laboratory data

Test/assessment	Required measurements	Recording	Analysis	Source data
Glucose absorption	PD fill volume. Glucose volume exact . Drain volumes (peritoneal drain + Carry life UF drain bag). Glucose concentration of drain volumes (peritoneal drain + Carry life UF drain bag).	In-clinic (Carry Life UF treatments) Home phase efficacy evaluations treatments (control and Carry Life® UF).	Sum of glucose added (PD fill volume (ml) * glucose concentration of PD solution (13.6 or 22.6 g/ml) + Glucose volume exact (ml) * 0.5 g/ml) minus the sum of glucose drained (peritoneal drain volumes * the glucose concentration of drain volumes (g/ml)).	Work sheets for measured data, laboratory data and eCRF for calculated data.

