#### 6.2.11 Other materials/products required for the clinical investigation

**Table 9. Products used in the clinical investigation**

Product	Procedure
A permanent PD catheter	Available in situ and used to perform the subject's standard PD therapy.
A Baxter MiniCap extended life PD transfer set with twist clamp	The Baxter MiniCap extended life PD transfer set with twist clamp is part of the patient's standard PD treatment. Each transfer set is used normally used for several months before it is exchanged.
Standard Baxter 1.36%/1.5%* glucose PD solutions	Initial fill prior to starting the Carry Life® UF treatment and according to the patient's standard PD prescription during the study.
Standard Baxter 2.27%/2.5%* glucose PD solutions	Used for the PET treatment (Visit 2) and according to the patient's standard PD prescription during the study.
50% glucose (500 g per L) solution for infusion in the Freeflex bag (Fresenius Kabi)	Added to the PD solution by the Carry Life® UF system during treatments.

\* 1.5% monohydrated glucose (Dianeal) is equivalent to 1.36% anhydrous glucose (Physioneal) and 2.5% monohydrated glucose (Dianeal) is equivalent to 2.27% anhydrous glucose (Physioneal).

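### The two EDC constants for the 50% glucose solution (0.5 g/ml and 1.2235 g/ml) fit together only if dissolved glucose takes up about 0.55 ml/g; if it takes up more, device-arm glucose UF efficiency is modestly overstated

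*Protocol*

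**What the plan says.** Section 8.1 of the protocol lists the constants from which the EDC will calculate endpoint measures. Two of them describe the same solution: "50% glucose solution concentration: 0.5 g/ml" and "Density 50% glucose solution: 1.2235 g/ml".

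Table 7 (section 6.2.8) uses them one after the other:

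- The exact glucose volume is "Weight of full glucose bag minus weight of used glucose bag (g) divided by the density of the 50% glucose solution (1.2235 g/ml").
- In the glucose absorption row, that volume enters as "ml) * 0.5 g/ml) minus the sum of glucose drained".

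The exact glucose volume is also subtracted in the formula for exact UF volume. Table 7 records it only for the in-clinic Carry Life UF treatments and the Carry Life UF efficacy evaluation treatments.

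The strength of the product is given as mass per volume throughout. Section 2.1 has "A 500 mg/ml, 500 ml Glucose Fresenius Kabi solution for infusion", and Table 9 has "50% glucose (500 g per L) solution for infusion in the Freeflex bag (Fresenius Kabi").

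**The concern.** Infused glucose is calculated as weight loss × 0.5 / 1.2235, so the two constants have to be right as a pair. Together they describe a solution that is 40.9% glucose by weight and in which dissolved glucose takes up unusually little room. The same density fits more easily if 50% is read as percent by weight. A density for a weight-based strength may therefore have been applied to a product defined per volume.

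Absorbed glucose is the denominator of glucose UF efficiency, which is a tested secondary endpoint (sections 5.2 and 7.1.7.3) and a performance claim to be verified (section 5.3). The control dwell has no glucose bag. An error in the density would therefore not cancel in the paired comparison, and more subjects would not reduce it.

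**Working it through.** **Inputs from the protocol.** Concentration 0.5 g/ml and density 1.2235 g/ml (section 8.1, Table 7). Doses of 11 and 15 g/h for 5 hours, i.e. 55 g and 75 g. Pilot results from section 3.8: UF 646 ml and efficiency 17.0 ml/g at 11 g/h; 739 ml and 14.5 ml/g at 14 g/h; control efficiency 5.9 ml/g.

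**Assumptions, not in the protocol.** Water density 0.998 g/ml. Volume taken up by dissolved glucose, v, of 0.60-0.65 ml/g.

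**1. The protocol's own figure.** Table 7 gives nominal volumes of 110 and 150 ml. These follow from the concentration: 55/0.5 = 110 ml and 75/0.5 = 150 ml. They agree with 500 g per litre and do not involve the density.

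**2. What the pair implies.** One millilitre weighs 1.2235 g and holds 0.5 g glucose, so it holds 0.7235 g water.
- Share by weight: 0.5/1.2235 = 40.9%.
- Volume per gram of glucose: (1 − 0.7235/0.998)/0.5 = 0.550 ml/g (0.543-0.553 for water densities of 0.993-1.000 g/ml).
- Same density, solution taken as 50% by weight: (1/1.2235 − 0.5/0.998)/0.5 = 0.633 ml/g (0.628-0.635 over the same water densities).

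**3. Density of a 0.5 g/ml solution under the assumption.** Density = 0.5 + (1 − 0.5v) × 0.998. The share of the infused amount that the EDC counts is density/1.2235.

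| v (ml/g) | density (g/ml) | share counted | under-count | of 55 g | of 75 g | of 110 ml | of 150 ml |
|---|---|---|---|---|---|---|---|
| 0.60 | 1.1986 | 0.980 | 2.0% | 1.1 g | 1.5 g | 2.2 ml | 3.1 ml |
| 0.65 | 1.1737 | 0.959 | 4.1% | 2.2 g | 3.1 g | 4.5 ml | 6.1 ml |

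At v = 0.55 the formula gives 1.2235 and the under-count is nil.

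**4. Effect on glucose UF efficiency.** Absorbed glucose is glucose added minus glucose drained, so an error of fixed size in the first term is a larger share of the difference. Pilot absorption is approximated as mean UF divided by mean efficiency.
- 11 g/h: 646/17.0 = 38.0 g absorbed. The EDC would count 38.0 − 1.1 = 36.9 g down to 38.0 − 2.2 = 35.8 g. From the denominator alone, efficiency is multiplied by 1.03-1.06. With the Table 7 UF shift as well, (646 + 2.2)/36.9 = 17.6 and (646 + 4.5)/35.8 = 18.2 ml/g, an overstatement of about 3-7%.
- 14 g/h: 70 g infused and 739/14.5 = 51.0 g absorbed. The under-count is 1.4-2.8 g, and the same calculation gives about 15.0-15.5 ml/g, again 3-7%.
- If the pilot figures already contain the error, the correction runs the other way: 17.0 becomes about 15.9-16.4 and 14.5 becomes about 13.6-14.0 ml/g. The relative size is the same.

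**5. Effect on UF volume.** Table 7 subtracts the exact glucose volume in ml, so the under-counted volume is added to device UF: 2.2-4.5 ml at 11 g/h and 3.1-6.1 ml at 15 g/h. The superiority margin is 250 ml.

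**The case against.** The strongest reply is that nothing in the protocol contradicts 1.2235 g/ml. The figure stands unchanged in both places, and no other density, percentage by weight or volume per gram of glucose is given. The conflict appears only once 0.60-0.65 ml/g is brought in from outside. This stands, and it is why the point is conditional. It does not remove the point, because the constants disagree over the whole of that range.

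Two stronger readings are tempting. A reader might infer that the pair is physically impossible, since 0.55 ml/g corresponds to 1.8 g/ml, above an assumed 1.5-1.6 g/ml for solid glucose. That is not a sound test: the accepted lower end of 0.60 ml/g corresponds to 1.67 g/ml, which exceeds the same solid density. A reader might also infer that the density is right and the solution really is 50% by weight. The concentration would then be 0.5 × 1.2235 = 0.612 g/ml, infused glucose would be under-counted by about 18%, and efficiency overstated by about 31-32%. The protocol gives no support for this: sections 2.1 and 8.1, Table 7 and Table 9 all describe 500 g per litre, and the nominal volumes follow from it.

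Three limits on the size also stand. The pilot absorption figures divide a mean by a mean of ratios with wide spread (SD 10.6 and 7.7 ml/g), so they are approximate. The pilot used 14 g/h, not 15 g/h. The UF shift exists only while UF is calculated with glucose volume in ml; if UF were calculated in grams throughout, the density would drop out of it, though not out of the glucose mass.

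**Conclusion.** The point holds conditionally. The formula chain, the 500 g per litre strength and the restriction to Carry Life UF treatments are all in the protocol. That the density is too high rests on the assumed 0.60-0.65 ml/g. On that assumption infused glucose is under-counted by about 2-4%, device-arm efficiency is overstated by roughly 3-7%, and device UF is overstated by about 2-6 ml under the Table 7 formula.

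The direction always favours the device, but the size is small. A reader might infer that the efficiency result or the primary endpoint is in doubt; the figures do not support that. The pilot contrast remains about 16 against 5.9 ml/g at 11 g/h, and 6 ml is under 3% of the 250 ml margin. What is affected is the accuracy of the reported device efficiency and its confidence interval. A constant that is probably wrong, and easy to check, should not be left in the endpoint calculation.

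**What to change.** Check the density of the 500 mg/ml product against its specification, or weigh a known volume from a bag. Then correct whichever constant proves wrong, in both Table 7 and section 8.1, before the calculations are locked. If 1.2235 g/ml is confirmed for this product at 0.5 g/ml, record the source and leave both constants as they are. If a constant changes, recalculate any stored values of exact glucose volume, glucose absorption, UF volume and glucose UF efficiency.

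The cost is one check, at most one constant in the EDC and two places in the text, with no new patient data. The downside for the sponsor is a slightly less favourable device efficiency.
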